# 1.8 Chapter Summary

Medication reconciliation is one of the key strategies to improve medication safety across transitions of care. Local healthcare providers find it difficult to retrieve previous medical records as the healthcare information system has not been integrated across the healthcare facilities in Malaysia. Thus, an electronic health record that aims to reduce medication discrepancies upon transition of care will be introduced. The study's findings are essential to healthcare professionals in implementing electronic health records. Due to the limited resources at healthcare facilities, healthcare professionals shall prioritise the patients that need medication reconciliation.

#### **CHAPTER 2**

#### **METHODOLOGY**

# 2.1 Study Design

Given the nature of the research question, a randomised controlled trial is developed to compare the prevalence of medication discrepancies in the first prescription upon transition of care from hospitals to primary health clinics between MedBook Portal and standard care. This study is a prospective and multicentre randomised controlled trial with a 1:1 allocation ratio to two groups, namely the intervention group and the control group. MedBook portal is a webpage that enables sharing of patient medication profile among healthcare facilities under the Ministry of Health.

# 2.2 Operational Definition of Terms

### 2.2.1 Medication Discrepancies

Medication discrepancy is defined as any variation or difference in medication regimen identified when comparing an old medication list and the newly prescribed medications.

### 2.2.2 Intentional Medication Discrepancy

Intentional medication discrepancy is defined as a justified discrepancy by a change in the patient's clinical condition.

# 2.2.3 Unintentional Medication Discrepancy

Unintentional medication discrepancy is defined as unjustified discrepancy after checking with prescriber. It is a medication error, specifically prescribing error.

# 2.2.4 Types of Medication Discrepancies

Medication discrepancy is classified into:

- i. Discrepant dose
- ii. Discrepant frequency
- iii. Polypharmacy
- iv. Drug Omission
- v. Drug Addition
- vi. Inappropriate drug

Table 2.1 lists the description and example of each type of medication discrepancy identified during medication reconciliation at hospital discharge. Table 2.2 lists the description and example of each type of medication discrepancy identified during medication reconciliation at the first follow-up at health clinics after discharge from the hospital. Figure 2.1 illustrates the example of medication discrepancies detected during medication reconciliation at hospital discharge and the first follow up at the health clinic.

 Table 2.1:
 Description And Example Of Each Type Of Medication Discrepancy

 Identified During Medication Reconciliation At Hospital Discharge

Type of	Description	Example
Medication		
Discrepancy		
Discrepant	A different dosage of a medication	A patient was treated with
dose	is prescribed in the discharge	Atorvastatin 20mg before admission
	prescription compared to the old	and during admission; however, the
	medication list in the medication	patient was discharged with
	history assessment form and	Atorvastatin 40mg.
	inpatient medication charts.	
Discrepant	A different frequency of	A patient was treated with
frequency	medication prescribed in the	Metoprolol 50mg OD before
	discharge prescription compared	admission. In the ward, the patient
	to the old medication list in the	has been given Metoprolol 50mg
	medication history assessment	BD and has been discharged with
	form and inpatient medication	Metoprolol 50mg BD.
	chart.	
Polypharmacy	Multiple agents from the same	Metoprolol is listed in the
	therapeutic class.	medication history assessment form.
		In the ward, Metoprolol is stopped,
		and the patient is started with
		Bisoprolol. During discharge,
		metoprolol is restarted and given
		together with Bisoprolol.

Table 2.1 continued

Drug	Medication is not prescribed in the	Metoprolol is listed in the
Omission	discharge prescription but is listed in the medication history assessment form and inpatient medication chart.	the ward and the patient is discharged without Metoprolol.
Drug Addition	Medication is prescribed in the discharge prescription but not listed in the medication history assessment form and inpatient medication chart.	
Inappropriate Drug	Any medication discrepancies that do not fit into any of the previously mentioned categories, such as a medication that no longer needed but is reordered in new prescription; a different formulation of the same item is prescribed.	Example 1:  A patient had diarrhoea in the ward and was given oral Loperamide 2mg TDS or PRN. However, Loperamide 2mg TDS was written on the discharge prescription when the patient no longer had diarrhoea.  Example 2:  A patient has been discharged with Chloramphenicol ear drops. However, the patient has an eye infection and was treated with Chloramphenicol eye drops in the ward.

Table 2.2:Description And Example Of Each Type Of Medication DiscrepancyIdentified During Medication Reconciliation At The First Follow-Up At HealthClinics After Discharge From The Hospital

Type of Medication Discrepancy	Description	Example
Discrepant dose	A different dosage of a medication is prescribed in the new prescription compared to the discharge prescription.	A patient has been discharged with Losartan 100mg. However, the new prescription on the first visit to the health clinic is Losartan 50mg.
Discrepant frequency	A different frequency of medication prescribed in the new prescription compared to the discharge prescription.	Ü
Polypharmacy	Multiple agents from the same therapeutic class.	Mefenamic acid and Diclofenac are prescribed concurrently.
Drug Omission	Medication is not prescribed in the new prescription but is listed in the discharge prescription.	A patient was discharged with Metoprolol, Losartan, and Metformin. However, only Metoprolol and Metformin are prescribed in the new prescription on the first visit to the health clinic.

Table 2.2 continued

Drug	Medication is prescribed in the	On the first visit to the health clinic,
Addition	new prescription but not listed in	the patient is prescribed with
	the discharge prescription.	Metoprolol, Losartan and
		Metformin. However, only
		Metoprolol and Metformin are listed
		in the discharge medication list.
Inappropriate	Any medication discrepancies that	Example 1:
Drug	do not fit into any of the previously mentioned categories, such as a medication that no longer needed but is reordered in new prescription; a different formulation of the same item is prescribed.	A patient has been discharged with Budesonide inhaler. However, the patient was prescribed with Budesonide nasal spray.  Example 2:  A patient has been discharged with Gliclazide 120mg MR OD. However, the patient was prescribed with Gliclazide 120mg OD in the new prescription on the first visit to health clinic.

[figure not shown]

Figure 2.1: Example of medication discrepancies detected during medication reconciliation

### 2.3 Study Population

The targeted population is the adult patients in Sarawak who are discharged from the public tertiary hospitals and referred to the public primary health clinics. These patients will continue to be treated at the selected public primary health clinics.

# 2.4 Study Sample and Locations

This study will be conducted in four public tertiary hospitals and ten public primary health clinics. The four public hospitals that cater for the patients from southern, central, and northern zones in Sarawak are selected. Those are Sarawak General Hospital (southern zone), Sibu Hospital, Sarikei Hospital (middle zone) and Miri Hospital (northern zone).

During this study, ten public primary health clinics which are located nearby to the four selected hospitals are chosen to follow up the participants who will be discharged and referred to these clinics. The healthcare facilities involved in this study are presented in Table 2.3. All patients who fulfil the selection criteria mentioned later will be invited to participate in the study.

**Table 2.3:** Public Major Hospitals and Health Clinics Involved in this Study

Public Major Hospitals	Public Primary Health Clinics
Sarawak General Hospital	Batu Kawa HC, Kota Sentosa HC, Kota Samarahan HC
Sibu Hospital	Jalan Oya HC, Lanang HC, Sibu Jaya HC
Miri Hospital	Miri HC, Tudan HC
Sarikei Hospital	Sarikei HC, Bintangor HC

#### 2.4.1 Inclusion criteria

Patients who fulfil the following criteria will be invited to participate in the study:

- i. Adult patients aged 18 years and above in general medical wards who had any of the following comorbidities: (1) cardiovascular related diseases, e.g.: hypertension, acute coronary syndrome, heart failure, stroke, atrial fibrillation; (2) endocrine related diseases, e.g.: diabetes, thyroid disorders; (3) renal related diseases, e.g.: chronic kidney disease, end stage renal failure; (4) respiratory related diseases, e.g.: asthma, chronic obstructive pulmonary disease.
- ii. Patients who are referred to the selected primary health clinics after hospital discharge.
- iii. Patients with home-based medical card.

### 2.4.2 Exclusion criteria

Patients discharged during public holidays or weekends will be excluded from this study.

#### 2.4.3 Withdrawal criteria

Patients readmitted to hospitals before the first review at the health clinic shall be withdrawn from the study. Patients can choose to withdraw at any time. Withdrawn patients will not be replaced.

### 2.5 Sample Size Calculation

This study aims to compare the prevalence of medication discrepancies in the first prescription upon transition of care from hospitals to primary health clinics between MedBook Portal and standard care. Hence, a two-tailed z-test of proportion between two groups with 80% power and a 5% of level significance will be used (10). The prevalence of medication discrepancies upon discharge reported in a previous study is 49% (8). We estimate the reduction of medication discrepancies via implementation of MedBook is 15%. Thus, a sample size of 322 subjects, 161 subjects in each group, is sufficient to detect a clinically importance difference of 15% between groups. However, with the estimation of a 20% loss to follow up, a total of 386 subjects will be recruited.

In addition, this study also aims to ascertain the prevalence of medication discrepancies and type of medication discrepancies in discharge prescription and in the first prescription upon transition of care from hospitals to primary health clinics. Sample size is calculated by using the following formula (11):

$$n = \frac{Z^2 P(1-P)}{d^2}$$

where n = sample size,

Z = Z statistic for a level of confidence,

P = expected prevalence or proportion

d = precision

By determining the Z = 1.96 for 95% CI and d = 0.05, the minimum sample size is 384. Based on the above sample size calculation, a total of 386 patients will be recruited. The sample size allocation for each hospital is determined on a pro-rata basis based on the total bed numbers in general medical wards and Bed Occupancy Rate (Table 2.4).

**Table 2.4:** Sample Size Allocation Of Each Hospitals

Public Major	Wards	Total	Bed	Sample
Hospitals		Bed	Occupancy	Size
		Numbers	Rate (%)	Allocation
Sarawak General	Male General Ward	48	114.4	144
Hospital	Female General Ward	48	102.0	
Sibu Hospital	Male General Ward 1	36	62.2	106
	Male General Ward 2	36	73.4	
	Female General Ward	32	83.5	
Miri Hospital	Male General Ward	29	114.1	72
	Female General Ward	30	62.8	
Sarikei Hospital	Male General Ward	35	82.4	64
	Female General Ward	35	50.2	
Total	-	329	-	386

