#### 2.7 Data and Instruments

#### 2.7.1 Data Collection Form

Medication discrepancies detected will be categorised according to the following groupings, discrepant dose, discrepant frequency, polypharmacy, drug omission, drug addition and inappropriate drug. Other data that will be collected include age, gender, number of medications, type of medication based on Anatomical Therapeutic Chemical (ATC) categorisation in Drug Formulary Ministry of Health Malaysia, comorbidities, and category of prescriber.

There are two electronic data collection forms using Google Form for data entry. The first data collection form (Appendix A) is administered by pharmacist at hospital before allocation. The second data collection form (Appendix B) is to be administered by pharmacist at the health clinic.

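### Section 2.5: 386 recruits leave about 309 after the plan's own 20% loss, short of its 322 for the primary comparison and its 384 for first-prescription prevalence; 161 per arm is itself slightly low

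*Combined protocol and SAP*

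**What the plan says.** Section 2.5 (Sample Size Calculation) makes two calculations and serves both with one recruitment figure.

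- **Primary comparison.** The method is "a two-tailed z-test of proportion between two groups with 80% power and a 5% of level significance will be used". The control rate of 49% is borrowed from discharge prescriptions in an earlier study, and the assumed reduction is 15%. Hypothesis H1a in Table 1.1 words this as a difference between rates, so the comparison is 49% versus 34%. The plan concludes that "a sample size of 322 subjects, 161 subjects in each group, is sufficient to detect a clinically importance difference of 15% between groups", and then that "with the estimation of a 20% loss to follow up, a total of 386 subjects will be recruited".
- **Prevalence.** A single-proportion formula is applied to overall prevalence and to the "type of medication discrepancies in discharge prescription and in the first prescription upon transition of care from hospitals to primary health clinics". The result is: "By determining the Z = 1.96 for 95% CI and d = 0.05, the minimum sample size is 384". The value of P is not stated. Recruitment stays at 386.

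Two other sections bear on this. Section 2.4.3 withdraws patients who are readmitted before the first clinic review and adds: "Withdrawn patients will not be replaced". Section 2.7.1 fixes the timing of the discharge measurement: "The first data collection form (Appendix A) is administered by pharmacist at hospital before allocation".

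**The concern.** Multiplying by 1.20 does not undo a 20% loss, because the loss is taken from the larger recruited number. The correct step is division by 0.80. The primary outcome is read at the first clinic visit, so every patient lost before then is lost to the primary analysis, and the plan rules out replacement.

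Two further points arise in the same section. The 161 per arm does not follow from the stated inputs, so correcting the inflation alone would not restore 80% power. And the 384 carries no loss allowance, although it is meant to cover the clinic prescription as well as the discharge prescription.

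What is at stake is the accuracy of two design claims. A non-significant primary result would be read against a power that the trial does not have, and the precision stated for first-prescription prevalence would be too favourable. The effect estimate is not biased by any of this.

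**Working it through.** **Inputs** (section 2.5 unless stated): control rate p1 = 0.49; difference 0.15 (also H1a), so p2 = 0.34; two-sided 5%; 80% power; 1:1 allocation (section 2.1); 322 evaluable; 20% loss; 386 recruited; no replacement (section 2.4.3); Z = 1.96 and d = 0.05 for precision. I assume that the 20% includes patients withdrawn for readmission; the plan does not say.

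**Step 1: inflation.**
- Plan's figure reproduced: 322 × 1.20 = 386.4, hence 386.
- Needed to keep 322: 322 / 0.80 = 402.5, so 403.
- Left from 386: 386 × 0.80 = 308.8, about 309 or 154 per arm, which is 13 below 322.
- Largest loss at which 386 still yields 322: 1 − 322/386 = 16.6%.

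**Step 2: the 161 per arm.** With z-values 1.960 and 0.842:
- Unpooled: (1.960 + 0.842)² × (0.49×0.51 + 0.34×0.66) / 0.15² = 165.5, so 166.
- Pooled, mean rate 0.415: [1.960 × √(2×0.415×0.585) + 0.842 × √(0.49×0.51 + 0.34×0.66)]² / 0.15² = 168.2, so 169.
- Other readings do not give 161 either: arcsine 168, continuity-corrected 182, one-sided 133, and 15% as a relative reduction 719.

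Recruits for 80% power after 20% loss: 332 / 0.80 = 415 (unpooled) or 338 / 0.80 = 422.5, so 423 (pooled).

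**Step 3: power for 49% versus 34%.**

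| Per arm | Pooled | Unpooled | Exact |
|---|---|---|---|
| 161 | 78.2% | 78.9% | 77.9% |
| 154 | 76.4% | 77.1% | 76.7% |

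- Recruiting 403 would restore only the first row, about 78–79%.
- At 154 per arm, 80% power is reached for a difference of 15.5 points (unpooled) to 15.7 points (pooled).
- 386 keeps 80% power only if loss is at most 1 − 332/386 = 14.0% (unpooled) or 1 − 338/386 = 12.4% (pooled).

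**Step 4: sensitivity to the control rate.** The 49% is a discharge figure used for a clinic visit. Assuming the same 15-point difference, pooled power at 154 per arm is:

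| Control rate | 40% | 45% | 49% | 55% | 60% |
|---|---|---|---|---|---|
| Power | 80.5% | 77.9% | 76.4% | 75.3% | 75.3% |

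**Step 5: precision.**
- Plan's figure reproduced: 1.96² × P(1−P) / 0.05² = 384.2 at P = 0.50 and 384.0 at P = 0.49.
- Discharge, measured on all 386: 1.96 × √(0.49×0.51/386) = ±4.99 points. Met.
- First clinic prescription, about 309: ±5.5 points at P = 0.415 (the mean of 49% and 34%), ±5.6 at P = 0.49 to 0.50. Not met.
- Even on 322 it would be ±5.4 to ±5.5, so most of the precision gap comes from the missing loss allowance on 384.
- 386 yields 384 clinic prescriptions only if at most 2 patients (0.5%) are lost. Keeping 384 after 20% loss corresponds to 384 / 0.80 = 480 recruits.

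**The case against.** No one disputes the arithmetic; the case on the other side is about weight.

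- **The deficit is small.** The inflation slip costs 13 patients and 1.3 to 1.8 points of power; with the low starting value the total is about 3 to 4 points. Section 2.13 plans reminders by message or telephone, and 386 still yields 322 if loss stays at or below 16.6%. This stands as a reason to call the shortfall modest. It does not make the statement correct, since 20% is the plan's own figure.
- **The assumed 49% matters more.** Moving the control rate between 40% and 60% shifts power by about 5 points, and at 40% the plan keeps 80% even after 20% loss. That is true, but the inflation error does not depend on the rate, and the stated power is for 49%.
- **161 is close.** It is 5 to 8 per arm short, and section 2.5 does not print its formula. It is fair to treat this as secondary; it matters mainly because 403 would not be enough either. Splitting the loss of power to tenths of a point should not be pressed, particularly for the exact test, where power moves in steps.
- **±5 points still holds for rarer types.** On 309 prescriptions it is met for any type with prevalence up to about 28%: 1.96 × √(0.28×0.72/309) = 5.0 points. H2a expects types from 5% to 60%, so this covers part of that range. The point stands, and the precision criticism is confined to overall prevalence and the commoner types.

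**Conclusion.** The concern holds. On its own inputs and its own loss estimate, section 2.5 delivers neither the 80% power nor, for overall first-prescription prevalence, the ±5 points that it states. The inflation error is certain and rests only on the plan's figures. The low starting value is a smaller, secondary error.

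The combined effect is power of about 76–77% at 49% versus 34%, and a half-width of ±5.5 to ±5.6 points rather than ±5. The discharge precision is sound. These figures assume a 20% loss split evenly between the arms and an absolute 15-point difference. The size is modest and the comparison is not biased, but the section should be corrected.

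**What to change.** Restate section 2.5, keeping 386:

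- Name the sample-size formula. For 49% versus 34%, two-sided 5%, 80% power, give 166 per arm (unpooled) or 169 (pooled) in place of 161.
- State that 386 recruits with 20% loss are expected to leave about 309 (154 per arm), which is below that number, and that this gives about 76–77% power for 49% versus 34%, or 80% power for a difference of about 15.5–15.7 points.
- For overall prevalence, limit ±5 points to the discharge prescription (386 patients) and state ±5.5 to ±5.6 points for the first clinic prescription (about 309). It may be added that ±5 points still holds there for types with prevalence up to about 28%.
- State the P used to obtain 384.

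The cost is wording only: the stated power and precision become slightly less favourable, with no extra patients and no change to design, conduct or primary analysis. The larger recruitment totals (403 to keep 322; 415 or 423 for full power; 480 for ±5 points at the clinic) are given for information and are not requested.

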# 2.6 Study Duration

This study is estimated to be conducted over 6 months, expecting to commence in August 2023.

#### 2.7 Data and Instruments

#### 2.7.1 Data Collection Form

Medication discrepancies detected will be categorised according to the following groupings, discrepant dose, discrepant frequency, polypharmacy, drug omission, drug addition and inappropriate drug. Other data that will be collected include age, gender, number of medications, type of medication based on Anatomical Therapeutic Chemical (ATC) categorisation in Drug Formulary Ministry of Health Malaysia, comorbidities, and category of prescriber.

There are two electronic data collection forms using Google Form for data entry. The first data collection form (Appendix A) is administered by pharmacist at hospital before allocation. The second data collection form (Appendix B) is to be administered by pharmacist at the health clinic.

#### 2.7.2 MedBook Portal

MedBook portal (https://aplikasi.jknsarawak.moh.gov.my/medbook) is a webpage that enable sharing of patient medication records among healthcare facilities under Ministry of Health. Sarawak State Health Department owned and managed this portal. All the information is kept under their server. Doctors in the Health Clinics and Study Pharmacists will be given access to this portal whereby each of the healthcare providers shall log in using their Identification Number and the password created by them. Doctor shall log in to MedBook Portal to check on discharge medication list when reviewing the patient at health clinic. MedBook Portal can be accessed both using a smartphone or a computer. The design of MedBook Portal in the smartphone version is shown in Figure 2.2. The design of MedBook Portal in the computer version is shown in Figure 2.3.

During the discharge process, the study pharmacist at hospital will upload the discharge prescription to MedBook Portal for both the control group and intervention group. When uploading the discharge prescription, the study pharmacist shall select the radio button 'intervention' for patients in the intervention group. MedBook Portal allows doctors at health clinics to view the prescription under the intervention group only. Whereas pharmacists at health clinics can view all the prescriptions in both groups. This setting is done based on the user role in MedBook Portal. The purpose of the setting is to ease the study pharmacist at the health clinic to compare the discharge prescription in MedBook Portal and the first prescription at the health clinic to identify medication discrepancies in both groups.

[figure not shown]

Figure 2.2: MedBook Portal in smartphone version

[figure not shown]

Figure 2.3: MedBook Portal in computer version

#### 2.7.3 MedBook Portal Notice

A MedBook Portal Notice will be placed in front of the patient's home-based medical card. Only patients in the intervention group are given MedBook Portal Notice. Hence, the doctors and pharmacists at health clinics can identify the recruited patients in the intervention group. The layout of the MedBook Portal Notice is shown in Figure 2.4.

[figure not shown]

Figure 2.4: MedBook Portal Notice

